2.2.2 Secondary Objectives

The secondary objectives of the study are to:

- Assess trough concentrations, accumulation, and apparent terminal half-life of MPA, and the impact of subcutaneous injection site (abdomen, upper thigh, or back of the upper arm) on these parameters, when Sayana® Press is injected every 4 months for 12 months of use
- Evaluate the safety of Sayana® Press when injected every 4 months for 12 months of use
- Evaluate the acceptability of Sayana® Press when injected every 4 months for 12 months of use

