10.7.2 Planned Method of Analysis

Serum MPA concentration data falling within defined sampling windows will be summarized graphically using box plots, by SC injection site and overall. Trough concentrations at months 4, 8, and 12 will also be summarized using geometric means, standard deviations, and percent coefficient of variation. Month 2, 3, and 4 data will be used to estimate $t_{1/2}$ based on random effects log-linear models (under the assumption that the terminal phase of absorption begins by month 2), including random intercept and

slope terms. Accumulation of MPA concentrations at months 8 and 12 will be estimated according to the ratio of trough concentrations and using the formula $R=[1-(0.5)^{\text{dosing interval/half-life}}]^{-1}$, where the dosing interval is 126 days. Anatomical sites of injection will be compared by computing 95% confidence intervals for geometric mean ratios of $t_{1/2}$ and trough concentrations. The effects of site, body mass index, and age on PK of MPA will be explored graphically and using analysis of covariance.

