Treatment will begin in the first 5 days of menses. A single MPA serum sample will be collected from all participants at baseline. All participants will be scheduled to receive re-injections at month 4 (approximately 17 weeks after treatment initiation) and month 8 (approximately 35 weeks after treatment initiation) and complete their planned follow-up at month 12 (approximately 53 weeks after treatment initiation). There will be a plus 7-day grace period for re-injections, but women who are up to 28 days late may continue treatment if they have a negative urine pregnancy test. Urine pregnancy testing will be performed at month 4, at study exit, at month 8 if the participant is more than 7 days late for her visit, and at any time during the study if clinically indicated. Participants will be evaluated for injection site reactions and asked to provide information on adverse events, prohibited concomitant medications and other contraceptive use, vaginal bleeding, and method acceptability at months 4, 8 and 12. Information on adverse events and use of any prohibited concomitant medications will be recorded if reported by participants at month 2 and 3 PK visits and at any unscheduled visits.

III. General Analytic Considerations

A. Study Size and Power

The sample size of 710 women receiving injections in the abdomen or upper thigh is expected to be sufficient to ensure that the difference between the estimated Pearl Index (pregnancies per 100 woman-years of use) and the corresponding upper 95% confidence bound does not exceed 1.0, so long as the observed Pearl Index is less than 0.75 and at least 80% of participants complete 12 months of follow-up. (The study has a 90% chance of achieving this precision target if the true (unobserved) pregnancy rate is no more than 0.5 per 100 women-years). In

addition, a cohort of 120 women (40 receiving injections in each the abdomen, upper thigh, and back of the upper arm) is sufficient to provide 85% power to detect 30% relative differences in PK parameters between injection sites, assuming the coefficient of variation is no more than 40% and using two-sided 0.05 level significance tests.

B. Data Source

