Serum MPA concentrations that fall within defined sampling windows (see Appendix A) will be summarized by timepoint and injection site in the following ways: 1) graphically using box plots with whiskers extending to 5th and 95th percentiles, and 2) in tables using means, geometric means, quartiles, minima, maxima, standard deviations, and percent coefficients of variation. A listing of all MPA concentrations for each participant will be provided along with an indication of any that fall outside of defined sampling windows, or any excluded from the PK Analysis Set due to concomitant medication use, injection in an anatomical site different from the site used at enrollment, or insertion of multiple Sayana Press units at the time of injection. The listing will also include subject age and BMI at time of sampling.

Month 2, 3, and 4 data will be used to estimate the apparent half-life for each injection site based on mixed-effects log-linear models with random intercept and slope terms, under the assumption that the terminal phase of absorption begins by month 2.⁵ Unique variance components will be used for each injection site, and observations falling outside sampling windows will not be excluded. The estimated slope (*m*) for each injection site will be used to calculate the apparent half-life according to the following formula: $half-life = \ln(2)/(-m)$. Pharmacokinetics in the terminal phase will be compared across injection sites based on overall and, if significant at the 0.05 level, pairwise Wald-type tests of differences in fixed-effects intercepts and slopes. Differences in variance components (both within-and between-subject effects) will similarly be assessed using likelihood ratio-tests.

Accumulation of MPA concentrations at months 8 and 12 will be estimated for each injection site by calculating the geometric mean ratio (GMR) of trough concentrations at 8 or 12 months to the trough concentration at 4 months, using mixed-effects models to compute 95% CIs of each GMR (with unspecified covariance of log-transformed repeated measures). Any MPA concentrations that are measured more than 7 days past a participant's scheduled injection date (along with any future measurements) will be excluded from the above accumulation

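### SAP X.A drops, without a recorded reason, the between-site ratios and confidence intervals for trough and half-life that Protocol 10.7.2 plans

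*SAP*

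**What the plan says.** The secondary objective (Protocol 2.2.2, repeated in SAP X) names three PK parameters: trough, accumulation and half-life. It then asks for "the impact of subcutaneous injection site (abdomen, upper thigh, or back of the upper arm) on these parameters".

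Protocol 10.7.2 states the method: "Anatomical sites of injection will be compared by computing 95% confidence intervals for geometric mean ratios of $t_{1/2}$ and trough concentrations".

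SAP X.A states a different one: "Pharmacokinetics in the terminal phase will be compared across injection sites based on overall and, if significant at the 0.05 level, pairwise Wald-type tests". The quantities tested are fixed-effect intercepts and slopes, and the data are limited: "Month 2, 3, and 4 data will be used to estimate the apparent half-life for each injection site based on mixed-effects log-linear models". Variance components are compared across sites by likelihood-ratio tests.

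The GMRs in SAP X.A are accumulation ratios within each site: "geometric mean ratio (GMR) of trough concentrations at 8 or 12 months to the trough concentration at 4 months". Concentrations at each timepoint are summarized by injection site with box plots and descriptive statistics. The mixed models for month 4, 8 and 12 troughs name study center, BMI and age as covariates, but not injection site.

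SAP III.A keeps the protocol's sizing statement that 40 women per site are "sufficient to provide 85% power to detect 30% relative differences in PK parameters between injection sites", at a CV of at most 40% and two-sided 0.05 tests.

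Protocol 10.13 lets deviations be recorded in an amendment, the SAP or the study report, together with their reasons. SAP I calls the SAP an expanded version of the protocol's plan. Neither SAP X.A nor the change log in SAP XVI.B mentions this departure.

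**The concern.** The upper-arm group was added to see whether its PK differs enough to affect the re-injection grace period, and Protocol 3.2 bases that period on estimated troughs and half-life. A decision of that kind is helped by knowing how large a difference between sites is and how uncertain it is. A Wald test gives a p-value, and a non-significant overall test is not evidence that sites are alike.

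If the SAP is followed as written, the report will contain no planned site-to-site ratio with an interval for any of the three parameters. Month 8 and 12 troughs, which reflect repeated dosing, enter no between-site inference. A reader of the SAP would not know that the protocol had planned otherwise.

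**Working it through.** **1. The two plans side by side**

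| Item | Protocol 10.7.2 | SAP X.A |
|---|---|---|
| Half-life between sites | GMR with 95% CI | Wald test of slopes, pairwise only after a significant overall test |
| Month 4 trough between sites | GMR with 95% CI | Enters the months 2–4 model; no trough contrast |
| Month 8 and 12 troughs between sites | GMR with 95% CI | Descriptive by site |
| Variability between sites | CVs and box plots by site | Likelihood-ratio tests |
| Accumulation | Trough ratios and formula | GMR with CI within each site, and formula |

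**2. The plan's power figure**

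Inputs (Protocol 10.1, SAP III.A): 40 per site, ratio 1.30, CV 40%, two-sided 0.05.

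- Log-scale SD = √ln(1 + 0.40²) = 0.385.
- SE of a pairwise log ratio = 0.385 × √(2/40) = 0.0861.
- ln(1.30)/0.0861 = 0.2624/0.0861 = 3.05.
- Power = 86.1% (normal) or 85.3% (noncentral t, 78 df).

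The stated 85% is therefore an ungated pairwise comparison on the ratio scale. The raw-scale alternative (difference 0.30, SD 0.40) gives 91% to 92%.

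**3. Cost of the gate**

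The overall-then-pairwise rule was simulated on such a parameter (400,000 runs, known variance). Ungated power for the 1.30 contrast was 86.2%.

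- One site differs from two equal sites: 83.1% with the gate.
- Third site midway on the log scale: 77.5% with the gate.

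The loss is 3 to 9 percentage points.

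**4. Precision of a restored trough GMR**

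CI factor = exp(1.96 × SE), with 40 per site unless stated.

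- CV 40% at both sites: exp(1.96 × 0.0861) = 1.18 (1.19 with t). With the t factor, an observed GMR of 1.00 gives 0.84 to 1.19, and 1.30 gives 1.10 to 1.54.
- 32 evaluable per site (an assumption of 80% retention; the documents give no PK dropout): factor 1.21 with t, power about 78%.

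The three-month trough means and SDs tabulated in Protocol 1.3.2.1 give other CVs:

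- Upper arm 0.35/0.43 = 81%, log variance 0.508.
- Abdomen 0.22/0.47 = 47%, log variance 0.198.
- Thigh 0.12/0.41 = 29%, log variance 0.082.

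| Contrast | SE | CI factor | Power for ratio 1.30 |
|---|---|---|---|
| Arm vs abdomen | √((0.508+0.198)/40) = 0.133 | 1.30 | about 51% |
| Arm vs thigh | √((0.508+0.082)/40) = 0.121 | 1.27 | about 58% |

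The width for a half-life ratio cannot be computed, because it depends on slope standard errors that the documents do not give.

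**5. Can the intercept test stand in for a trough test?**

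SAP X.A does not state the model's time origin. Take half-lives of 80.9 days (thigh) and 103.7 days (abdomen) from the same table, and equal concentrations at day 119. The slope difference is ln2 × (1/80.9 − 1/103.7) = 0.00188 per day. The intercept ratio is then exp(0.00188 × days from the origin to day 119):

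- origin at day 0: 1.25
- day 61: 1.12
- day 91: 1.05
- day 119: 1.00

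What the intercept test means therefore depends on a choice the SAP leaves open. Only an origin at day 119 makes it a test of the month 4 level.

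**The case against.** The other side has several good points.

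- **Estimates by site survive the gate.** A reader might infer that a non-significant overall test leaves the objective with no estimate. It does not. The gate applies only to the pairwise tests. Half-lives, geometric means, CVs and accumulation GMRs with intervals are reported for each site regardless, and point ratios follow by division. The planned interval on the ratio is what is missing.
- **Month 4 is not ignored.** A reader might infer that troughs play no part in the comparison. Month 4 values are in the terminal-phase model, and intercept and slope together fix the fitted month 4 level.
- **Half-life is tested.** A reader might infer that the 85% power has no matching analysis at all. Half-life is ln(2)/(−slope), so the slope test is a test of half-life. Trough has no matching test.
- **The 25% intercept difference is conditional.** It holds only for an origin at day 0, which the SAP does not state. The half-lives come from 12 women per site, and in that example the sites' PK truly differs. It is no evidence of a false finding.
- **Variability is covered.** Protocol 3.2 also wants the upper-arm group to confirm greater variability. The SAP's variance-component tests and 5th-percentile whiskers serve that aim, and a GMR would not.
- **Departure is allowed.** Protocol 10 calls its text a summary, and Protocol 10.13 permits deviations. The SAP change log covers only changes after version 1.0, so its silence cannot date the departure. Protocol 10.13 still asks for reasons. The SAP gives none, although the study report could.

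These points limit the concern. None of them supplies the between-site ratios and intervals that Protocol 10.7.2 specifies.

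**Conclusion.** The SAP omits, with no recorded reason, the between-site GMRs and 95% intervals for half-life and trough that the protocol specifies. No other SAP section supplies them. As written, the objective on injection site has descriptive results by site and hypothesis tests, but no planned between-site estimate with an interval, no direct trough contrast at month 4, and no between-site inference at months 8 or 12.

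The gate's own cost is modest (3 to 9 points of power under the simulated patterns). The main loss is the missing estimates and intervals. A restored trough GMR would have an interval of about ×/÷1.18 if 40 women per site are evaluable and the CV is 40%. Upper-arm contrasts would be nearer ×/÷1.27 to 1.30 if the earlier three-month CVs carry over. Those CVs come from small separate studies (25 women for the arm, 12 each for thigh and abdomen) and rest on a log-normal conversion.

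This affects a secondary objective, not the primary Pearl Index, and it should be corrected.

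**What to change.** In SAP X.A:

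1. Fit a log-trough mixed model to months 4, 8 and 12 with injection site and site-by-visit terms and site-specific variances. Report pairwise between-site GMRs with 95% CIs at each month.
2. Report pairwise half-life ratios from the fixed-effect slopes, with 95% CIs by the delta method or bootstrap. Label them ratios of model-based half-lives, since they are not strictly geometric mean ratios of individual half-lives.
3. Report all of these whatever the overall test shows.
4. Keep the variance-component tests, which answer a separate question.
5. State the time origin of the terminal-phase model. Centring at day 119 makes the intercept the month 4 level.
6. List the revision in the change log. If the sponsor prefers the current tests, record the departure and its reason as Protocol 10.13 requires.

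The cost is SAP wording, some programming and one table, all from samples already planned. The downside is one more table of unadjusted secondary comparisons, which is consistent with SAP III.E.

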1.4.1.2 Injection Site Reactions

Clinical trials have demonstrated that there is a small risk of injection site reactions (ISRs) for Depo-subQ Provera 104®. In 5 clinical studies involving 2,325 women (282 treated for up to two injection intervals; 1,780 treated for up to four injection intervals; and 263 women treated for up to 8 injection intervals), 5% reported ISRs and 1% had persistent skin changes, typically described as small areas of induration or atrophy [12, 16]. A retrospective study based on individual case safety reports of women receiving Depo-subQ Provera 104® identified 398 injection site reactions reported to the WHO VigiBase through January 2016. Notably, the rate of ISRs in the retrospective study could not be quantified due to the unknown total number of women and injections [22].

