10.8.2 Safety Analysis

All SAEs, AEs leading to product withdrawal, and AEs that are Grade 1 or higher ISRs will be coded by a trained medical coder at FHI 360 using the Medical Dictionary for Regulatory Activities (MedDRA) by preferred term and system organ class. The numbers and percentages of participants experiencing AEs leading to product withdrawal and AEs that are Grade 1 or higher ISRs will be presented by severity. All relevant information on any deaths or other SAEs will be discussed in the subject narrative included in the clinical study report. Numbers and percentages of participants experiencing any ISR will be summarized by SC injection site, and ISRs will also be presented in a listing. Body weight, BP, and bleeding patterns will be summarized graphically or using shift-tables (i.e., change from baseline).

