Data management (DM) plans are detailed in a separate study-specific document. Briefly, study center data are recorded on paper case report forms (CRFs) which are scanned by the study centers and entered into a clinical database management system at FHI 360. Data will be verified by study monitors and appraised for consistency by FHI 360 DM staff using both automated logical checks and manual review. A trained medical coder at FHI 360 will code all SAEs, AEs leading to product withdrawal, and AEs that are Grade 1 or higher ISRs using the Medical Dictionary for Regulatory Activities (MedDRA). Any adjudication of estimated dates of fertilization or other endpoint data will be performed following FHI 360 Standard Operating Procedures (SOPs). A central laboratory (PPD Development) will perform serum MPA testing, with results transferred to FHI 360 DM via password-protected Excel files. FHI 360 DM will create SAS datasets (version 9.4 or higher) containing lab and CRF data for use by biostatisticians conducting interim and final analyses.

C. Missing Data

It is anticipated that some event dates required for safety analyses may be incomplete. Decision rules for how and when to impute such incomplete date fields will be developed and documented by the medical monitor when reviewing study data and be documented in any study report produced. All other missing data will be ignored (i.e., treated as missing at random) unless patterns are identified through exploratory analysis which suggest the potential for biased assessments of efficacy, safety, PK, or acceptability. In the event such patterns are identified, rules for imputing data will be clearly described and justified in the study report.

D. Covariate Adjustment

The primary efficacy analysis will adjust for study center through stratification. Any other adjustments for covariates are addressed in the relevant sections below.

E. Test Size and Confidence Levels

Unless otherwise noted, all confidence intervals reported for the primary, secondary, and subgroup analyses will be computed at the 95% coverage level, and all p-values will be assessed at the two-sided 0.05 significance level, with no adjustment for multiple testing.

IV. Randomization, Allocation Concealment, and Blinding

A. Randomization

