All participants will receive the same study drug, Sayana® Press, and will be randomized to receive their injections in one of three subcutaneous injection sites: abdomen, upper thigh, or back of the upper arm. One cohort of N=630 will be randomized 1:1 to receive their subcutaneous injections of Sayana® Press in the abdomen or upper thigh, and a second PK cohort of N=120 women who agree to serum MPA testing at 6 time points (baseline and

months 2, 3, 4, 8, and 12) will be randomized 1:1:1 to receive their injections in the abdomen, upper thigh, or back of the upper arm. Using this randomization scheme, 355 women will receive their injections in the abdomen, 355 in the upper thigh, and 40 in the back of the upper arm. Randomization in each cohort will use randomly-permuted blocks, stratified by study center and cohort with the following planned enrollment totals at each site: 250 at the center in Brazil (UNICAMP), 150 at the center in Chile (ICMER), and 350 at the center in the Dominican Republic (Profamilia). Within these totals, 42 at Profamilia, 36 at ICMER, and 42 at UNICAMP will be randomized in the PK cohort and the remainder of the enrollment total at each center will be randomized in the primary cohort. Randomization sequences will be created for each combination of study center and cohort by an FHI 360 Randomization Statistician using a validated program written in SAS® version 9.4 or higher. Recognizing that actual numbers of participants enrolled at each site may change during the enrollment period due to center performance or other issues, additional randomization numbers will be generated for the primary cohort within each center to allow one or two centers to expand enrollment to compensate for reduced enrollment at the remaining center(s)².

B. Allocation Concealment

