⁵ This assumption will be formally assessed using appropriate log-linear random-effects model diagnostics, and by comparing predicted month 8 and month 12 concentrations (based on the half-life estimates and 4-month data) with the observed month 8 and 12 concentrations.

analysis. Steady-state accumulation ratios will be estimated as $R = [1 - (0.5)^{\text{dosing interval/half-life}}]^{-1}$, where the dosing interval is assumed to be 126 days and the half-life is estimated in the method described above.

The effects of study center, BMI, and age on trough concentrations will be explored graphically and by incorporating covariates in mixed-effects models based on month 4, 8, and 12 data. Intra-subject variability across injection cycles may also be explored using MPA trough levels at months 4, 8, and 12.

B. Safety

Safety endpoints will include serious adverse events (SAEs), adverse events (AEs) leading to product withdrawal, injection site reactions, bleeding patterns, blood pressure, and body weight recorded at months 4, 8, and final visits. All SAEs, AEs leading to product withdrawal, and AEs which are Grade 1 or higher ISRs will be coded by a trained medical coder at FHI 360 using the Medical Dictionary for Regulatory Activities (MedDRA) to classify them according to preferred term and system organ class (SOC). Safety analyses will be performed using the Treated Population and Safety Analysis Set and will be based on treatment group actually received.

All relevant information on any SAEs will be discussed in the subject narrative included in any clinical study report and in a listing. Numbers and percentages of participants experiencing AEs (specifically AEs leading to product withdrawal and ISRs which are Grade 1 or higher) will be presented by severity, study center, and injection site. Percentages of participants experiencing specified AEs will be compared across injection sites (pooled over severity and study center) within each SOC using Fisher's exact tests. Listings of any AEs will include actual injection site, a description of AE, type of AE, days to onset, relatedness to Sayana Press, seriousness, severity, outcome, and duration. Numbers and percentages of participants experiencing ISRs of any grade will be summarized by injection site, and ISRs will also be presented in a listing.

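### Safety is compared between injection sites by percentages and Fisher tests, with no between-site difference or ratio and its confidence interval

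*SAP*

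**What the plan says.** SAP X.B presents numbers and percentages of women with AEs leading to withdrawal and with Grade 1 or higher ISRs by severity, center and injection site. It adds any-grade ISRs by injection site, listings and narratives for serious events. The only between-site inference is that percentages with specified AEs "will be compared across injection sites (pooled over severity and study center) within each SOC using Fisher's exact tests". Whether this is one three-group test or a set of pairwise tests is not stated. Groups are formed by treatment actually received. SAP III.E adds that "all p-values will be assessed at the two-sided 0.05 significance level, with no adjustment for multiple testing".

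Protocol 10.8.2 is purely descriptive here: "Numbers and percentages of participants experiencing any ISR will be summarized by SC injection site". It names no between-site test.

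Two other outcomes are handled differently. For pregnancy, SAP IX.C replaces the log-rank test with 95% intervals for rate ratios if events are too rare for the test. For PK, Protocol 10.7.2 compares sites by 95% intervals for geometric mean ratios. Safety has no counterpart to either.

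**The concern.** Injection site is the randomized factor, and ISRs are the safety events most directly tied to it. Protocol 3.2 notes that the product leaflet names only the abdomen and thigh, but that some providers use the upper arm. A reader of the results will therefore ask how large an excess of reactions at that site remains compatible with the data.

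Percentages and a p-value do not answer this. A non-significant test can come from a comparison that is informative or from one that is nearly empty, and the planned output does not distinguish them. What is at stake is interpretation: p > 0.05 in a 40-woman group could be taken as reassurance.

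**Working it through.** **Inputs.**
- Group sizes, SAP IV.A: "355 women will receive their injections in the abdomen, 355 in the upper thigh, and 40 in the back of the upper arm".
- Two-sided 0.05, unadjusted (SAP III.E).
- Reference ISR rate: the trial sets none. Protocol 1.4.1.2 reports, from earlier studies of the product, that "5% reported ISRs and 1% had persistent skin changes". The 5% is used here as an assumption and varied from 1% to 10%.
- Effect size: a doubling, chosen here for illustration. Neither document states a target difference for safety.

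**The plan's own power figure.** The only power stated for a site comparison is for PK (SAP III.A): "a cohort of 120 women (40 receiving injections in each the abdomen, upper thigh, and back of the upper arm") gives "85% power to detect 30% relative differences in PK parameters between injection sites", "assuming the coefficient of variation is no more than 40"%. On the log scale SD = √ln(1 + 0.4²) = 0.385 and δ = ln 1.3 = 0.262, so δ/SD = 0.681. With 40 per group, 0.681 × √(40/2) = 3.046, and Φ(3.046 − 1.96) = 86.1%. The t-test version gives 85.3%. The stated 85% reproduces, but it concerns PK. No power is stated for safety.

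**Probability that Fisher's test misses a doubling.** Miss rate = 1 − Σ P(x₁)P(x₂) over all outcome pairs with two-sided Fisher p ≤ 0.05, where x₁ and x₂ are binomial (exact enumeration).

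| Reference → doubled | Thigh vs abdomen (355 vs 355) | Arm vs abdomen (40 vs 355) | Arm vs both pooled (40 vs 710) |
|---|---|---|---|
| 1% → 2% | 88.7% | 94.1% | 91.3% |
| 4% → 8% | 44.3% | 78.8% | 77.3% |
| 5% → 10% | 32.5% | 74.4% | 73.4% |
| 8% → 16% | 10.8% | 66.1% | 62.8% |
| 10% → 20% | 4.3% | 57.9% | 55.6% |

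Arm vs thigh equals arm vs abdomen when both large sites are at the reference rate. The pooled contrast is not defined in the SAP and is shown only for comparison. If the SAP means one three-group test, simulation at 5% gives a miss rate of about 35% to 37% when one large site doubles and about 75% when only the arm doubles. If 80% of each group were evaluable (the completion figure in SAP III.A), the 5% row becomes 44% (284 vs 284) and 79% (32 vs 284).

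**What an interval would add.** Newcombe's interval for d = p₁ − p₂, with Wilson limits (l, u) for each proportion, is d − √[(p₁−l₁)² + (u₂−p₂)²] to d + √[(u₁−p₁)² + (p₂−l₂)²].

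- Thigh 18/355, abdomen 18/355 (5.07% each; Wilson 3.23% to 7.87%): d = 0, interval −3.35 to +3.35 points. A doubling (+5.07) is excluded.
- Arm 2/40 (5.00%; Wilson 1.38% to 16.50%), abdomen 18/355: d = −0.07. Lower: −0.07 − √(3.62² + 2.80²) = −4.65. Upper: −0.07 + √(11.50² + 1.84²) = +11.58. A doubling is not excluded.
- Thigh 36/355, abdomen 18/355: d = +5.07 (+1.16 to +9.09).
- Arm 4/40, abdomen 18/355: d = +4.93 (−1.73 to +18.11).

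The first two examples show near-identical percentages and no significant difference. Only the interval shows that one bounds an excess usefully and the other does not.

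**The case against.** The strongest reply is that the trial was never meant to compare safety between sites. Both documents attach the effect of injection site to the PK objective; the safety objective concerns the 4-month regimen. Protocol 3.7.1 justifies randomizing the site by its relation to efficacy and PK, and the 40 upper-arm women were added for PK. No safety margin, safety power or claim of similar safety appears. This stands: low power limits what a result can mean and is not an error in the plan.

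A reader might also infer more than the documents support:

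- *That safety by site rests on p-values alone, or that the report could say nothing beyond p > 0.05.* Counts and percentages by site are planned, so a raw difference can be read off and an interval computed later. What is missing is the pre-specified contrast with its interval.
- *That the miss rates are properties of the plan.* They depend on a background 5% that the trial does not adopt. Protocol 8.3 has injection sites examined at enrollment, re-injection and final visits with Grade 1 or higher recorded, so the rate here could differ. The tests are also run per SOC, and the figures apply to ISRs only if ISRs dominate the SOC to which they are coded.
- *That every comparison is weak.* For 5% versus 15% at 355 vs 355, power is 99.4%.

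The SAP's mock tables are separate and not available here. They might include intervals, but nothing in the SAP text says so.

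**Conclusion.** The gap is real and minor. SAP X.B supplies by-site percentages and Fisher tests but no between-site estimate with an interval, which departs from how the plan treats pregnancy and PK. With a 5% reference ISR rate, a doubling and pairwise tests, a non-significant result would occur despite a true doubling about one time in three for thigh versus abdomen and about three times in four for the upper arm. The first figure is highly sensitive to the assumed rate; the second stays above one half at every rate from 1% to 10%. The groups are taken at their planned sizes, whereas the analysis is by treatment received. The conclusion that intervals are absent needs none of these assumptions.

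**What to change.** In SAP X.B, for Grade 1 or higher ISRs and for AEs leading to withdrawal, add risk differences for thigh vs abdomen, upper arm vs abdomen and upper arm vs thigh, each with a 95% Newcombe score or exact interval. Keep the Fisher p-values as descriptive, and say whether they are overall or pairwise. Add a sentence that similar safety between sites will not be inferred from p > 0.05.

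The cost is SAP wording and extra columns in tables already planned; no new data are needed. The upper-arm intervals will be visibly wide. They make the imprecision plain but cannot reduce it.
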